The primary endpoints are glucose variability and changes detected by hypoglycemic fear survey. We will measure indices of glucose variability (mean glucose \pm SD, % of glucose within/above/below target ranges, J Index, High Blood Glucose Index [HBGI], Low Blood Glucose Index [LBGI], Mean Amplitude of Glycemic Excursions [MAGE], CONGA_n) throughout pregnancy using the SMBG 7-point profiles for one week taken once per trimester. Hypoglycemic fear survey results will be assessed once monthly over the pregnancy. We will compare outcomes within individuals over time and between individuals of the different study arms. We will test whether outcomes differ between women using Dexcom alone and women using Dexcom with Share™ using interaction terms, and will stratify analyses if differences by group are greater than 10 mg/dL in mean glucose levels are detected. Since SMBG logs will be taken at multiple time points over the pregnancy and since CGMs will be worn continuously for the duration of each pregnancy, linear mixed models will be used to assess changes in outcome measures (GV, time spent in target below or above target) over time in each trimester of pregnancy. We will use linear mixed models to assess changes in the hypoglycemic fear survey in each month of the pregnancy. Secondary endpoints include A1C differences among study arms. Improvement in glycemic variability parameters with a possible reduction of A1C by 0.3%, measured as the difference of the mean A1C laboratory values of the arms of the study between baseline (0-3 months, first trimester), second trimester (3-6 months), and third trimester (6 to 9 months). Mixed models account for missing data, allow for an unstructured covariance matrix for repeated measures, and account for inter-subjects correlation of measurements. Secondary outcomes will be used

in the same mixed models. Differences in frequency of low alert glucose rates, high alert glucose rates, and interventions for low or high glucose values among the followers for each study arm will be analyzed with student t-tests. A p-value < 0.05 will be considered significant, and we will perform statistical analyses with SAS software (version 9.3, SAS Institute, Cary NC).

Publication Strategy:

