Appendix E

Follower Questionnaire

Subject ID: _____

Clinic Visit: (dd/mmm/yyyy) : _____ / _____ / _____

Gestational Age of Pregnant Participant:

4 to 8 weeks 8 to 12 weeks 12 to 16 weeks 16 to 20 weeks 20 to 24 weeks

24 to 28 weeks 28 to 32 weeks 32 to 36 weeks 36 to 40 weeks 40 to 42 weeks

4 to 12 weeks post-partum

LOW GLUCOSE QUESTIONS

How many times were you alerted to low glucose levels this month?

Never 1-5x mo 1-5 x weekly Daily More than 1 x daily N/A

Did you intervene to help your pregnant partner with low glucose levels this month?

Yes No

If yes, how often?

Never 1-5x mo 1-5 x weekly Daily More than 1 x daily N/A

If yes, what was the nature of the intervention? Check all that apply.

Gave glucose tablets/gel Gave glucagon injection

Gave food or drink with carbohydrates Called health care provider

Checked blood glucose level Called emergency services (like 911)

Other (Please describe: _____)

How many times did your pregnant partner's low glucose levels interfere with her daily activities this month?

Never 1-5x mo 1-5 x weekly Daily More than 1 x daily N/A

HIGH GLUCOSE QUESTIONS

How many times were you alerted to high glucose levels this month?

Never 1-5x mo 1-5 x weekly Daily More than 1 x daily N/A

Did you intervene to help your pregnant partner with high glucose levels this month?

Yes No

If yes, how often?

Never 1-5x mo 1-5 x weekly Daily More than 1 x daily N/A

If yes, what was the nature of the intervention? Check all that apply.

Gave insulin shot Checked ketone level

Gave insulin through an insulin pump Called health care provider

Checked blood glucose level Called emergency services (like 911)

Other (Please describe: _____)

How many times did your pregnant partner's high glucose levels interfere with her daily activities this month?

Never 1-5x mo 1-5 x weekly Daily More than 1 x daily N/A

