 Jaundice	 Congenital anomalies _____	

Other _____

Was the baby admitted to the Neonatal Intensive Care Unit (NICU) for any length of time during your hospital stay? Yes No

If yes, please describe: _____

Are you or did you ever breastfeed after your baby was delivered? Yes No

If yes, check all that apply:

- Breastfed within the first week of baby's birth and not afterwards
- Breastfed within the first month of baby's birth and not afterwards
- Breastfed for the first 2 months after baby's birth and not afterwards
- Breastfed for the first 3 months after baby's birth and not afterwards
- Breastfed for the first 3 months after baby's birth and still breastfeeding
- Breastfed exclusively
- Breastfed and formula-fed the baby

Questions about glucose variability:

Have you had any glucose values below 50 within the last month? Yes No

If yes, how often on average?

- Every day
- A few times per week
- A few times per month
- Once

Over the last month did you have to do something to correct a low glucose (<50 mg/dL) or did someone else have to intervene for a low glucose on your behalf? Yes No

If yes, check all that apply:

- Consume glucose tablets or glucose gel
- Eat or drink something with carbohydrates
- Call health care provider for help
- Receive an injection of glucagon
- Receive an infusion of dextrose (glucose through a vein)
- Call to emergency services (like 911)
- Stay in the hospital for observation and/or treatment

If yes, when? _____ For how long? _____

Have you had any glucose values above 300 within the last month? Yes No

If yes, how often on average?

- Every day
- A few times per week
- A few times per month
- Once

Over the last month did you have to do something unusual (besides taking extra insulin) for a very high glucose (<300 mg/dL) or did someone else have to intervene for a very high glucose on your behalf?

Yes No

If yes, check all that apply:

- Take multiple insulin boluses within 6 hours to bring the glucose down
- Change an infusion set earlier than anticipated
- Drink extra amounts of fluids
- Call health care provider for help
- Call to emergency services (like 911)
- Receive insulin and/or fluids through a vein
- Stay in the hospital for observation and/or treatment

If yes, when? _____ For how long? _____

References:

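### The follower form's frequency bands overlap, leave a gap and have no upper limit, so the planned t-tests on follower rates have no defined numeric input; separately, one post-partum item has a reversed inequality sign.

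*Combined protocol and SAP*

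**What the plan says.** **Analysis.** The Statistical Analysis Plan sets out the follower comparison in one sentence. The quantities compared are "Differences in frequency of low alert glucose rates, high alert glucose rates, and interventions for low or high glucose values among the followers". The method is given at the end of that sentence: "for each study arm will be analyzed with student t-tests". The threshold follows: "A p-value < 0.05 will be considered significant". It does not say how a questionnaire answer becomes a rate.

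**Data source.** The protocol (follower schedule of events, Visits 3 through 13, Table 2) has each consenting main follower complete a questionnaire monthly. The form in Appendix E asks, for example, "How many times were you alerted to low glucose levels this month". All six frequency items (alerts, interventions and interference with daily activities, for low and for high glucose) offer the same answers: "Never 1-5x mo 1-5 x weekly Daily More than 1 x daily N/A". None asks for a number.

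**Other records.** Under Visits 3 through 13 and Visit 14, staff also record on source documents how often the subject needed an intervention in the previous month. For Group 2, interventions prompted by a Share alert are documented as well.

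**Post-partum form.** Appendix F is completed by the woman, not the follower. One item reads "Have you had any glucose values above 300 within the last month". The item on unusual action that comes after it and its frequency options is worded "for a very high glucose (<300 mg/dL) or did someone else have to intervene".

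**The concern.** A t-test needs one number per follower. The form yields a category, and the categories mix a monthly and a weekly scale without meeting cleanly. Whoever analyses the data must choose a score for each box after the forms are in, and different reasonable choices can give different answers.

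What is at stake is the first secondary objective: whether followers' remote monitoring leads to interventions for low and high glucose. For follower alerts, the documents describe no other source that covers all three arms, because followers in Groups 1 and 3 receive no data through a device. Any loss of information may also be uneven. Group 2 followers receive device alerts, so they may sit more often in the wide or unbounded upper boxes. That last step is my inference; the documents do not state it.

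The Appendix F wording is a separate matter: a live data-collection item whose sign contradicts its own words.

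**Working it through.** **The plan's own figures.** No rate, SD, effect size or power is stated for any follower outcome, so there is nothing to reproduce on this point. The only sample-size arithmetic, 40 × 0.20 = 8 drop-outs and 40 − 8 = 32 completers, is correct but does not bear on it.

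**Step 1: put the boxes on one scale.** Inputs: the answer options in Appendix E. Assumption: month length, which the documents do not define, taken as 28, 30, 30.44 or 31 days. With W = days ÷ 7 weeks in a month, the monthly box is 1 to 5 events, the weekly box is 1 × W to 5 × W, and the daily box is one event per day.

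| Days in month | W | Weekly box, events per month | Counts fitting both 1–5 boxes | Counts fitting no box | Six a week, per month |
|---|---|---|---|---|---|
| 28 | 4.000 | 4.0–20.0 | 4, 5 | 21–27 | 24.0 |
| 30 | 4.286 | 4.3–21.4 | 5 | 22–29 | 25.7 |
| 30.44 | 4.348 | 4.3–21.7 | 5 | 22–30 | 26.1 |
| 31 | 4.429 | 4.4–22.1 | 5 | 23–30 | 26.6 |

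Five a month is ambiguous and six a week has no box, whichever month length is used.

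**Step 2: width.** Each 1–5 box spans a ratio of 5. In a 30.44-day month, two followers in the weekly box can differ by 21.74 − 4.35 = 17.4 events and look identical. The top box has no upper limit.

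**Step 3: what an arm comparison can recover.** Suppose every follower in one arm ticks the monthly box and every follower in another ticks the weekly box (30.44-day month). The true difference in mean rate lies between 4.35 − 5 = −0.65 and 21.74 − 1 = 20.74 events a month. The ordering is nearly settled; the size is not. If anyone ticks the top box, the arm mean has no upper bound.

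**Step 4: does the scoring matter?** Hypothetical data: in arm A half the followers answer never and half daily; in arm B all tick the weekly box.
- Midpoint scores (0, 3 × 4.348 = 13.0, 30.44): A = (0 + 30.44) ÷ 2 = 15.2; B = 13.0. A is higher.
- Rank scores (never 0, monthly 1, weekly 2, daily 3): A = (0 + 3) ÷ 2 = 1.5; B = 2.0. B is higher.

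The same answers reverse direction. The plan prescribes neither scoring; the example shows only that the choice can decide the result.

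**Step 5: zero and not applicable.** The form offers both a never box and a not-applicable box without distinguishing them, and repeats both after the respondent has said that she or he did intervene. One is a zero and the other is presumably missing, so the difference changes any mean.

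**Step 6: Appendix F, side by side.** The earlier item asks about values above 300. The later item speaks of a very high glucose, puts a less-than sign before 300 in the parenthesis, and lists actions taken for high glucose. The sign is at odds with the item's own adjective, its response list and its neighbour.

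**The case against.** Several points on the other side stand.

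- **The data are not lost.** The boxes are ordered and support an ordinal comparison or bounds. For interventions, subject-reported frequency is also on source documents, although that is the woman's report and not the follower's. A reader might infer that the rates are irrecoverable altogether. The documents support only that numeric follower rates cannot be derived from this form.
- **The overlap and the gap are narrow.** The overlap is a single count, or two in a 28-day month, and an item about the current month makes the monthly box the natural answer for five. The box widths, the open top and the missing scoring rule carry more weight.
- **Selected cases can mislead.** A fall from 16 to 8 a month stays in the weekly box, which might suggest that a halving would show as no change. A fall from 6 to 3 does change box, and one follower's unchanged answer says little about an arm. Likewise, five events scored 3 or 13.0 differ 4.3-fold only under midpoint scoring, which the plan does not prescribe.
- **Bands are a legitimate choice** for lay recall over a month. A whole-number count invites rounding when alerts come daily or more often.
- **The Appendix F sign does not touch the follower rates.** It sits in a yes/no item on the woman's form. Taken literally, it might seem to count almost every woman and miss the intended events. But the item still requires unusual action for a very high value and comes after an item about values above 300. Most women would probably read it as intended.

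None of this supplies the numeric input or scoring rule that the planned t-test needs.

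**Conclusion.** The point holds for the follower form. The planned t-tests on follower alert rates and intervention frequencies rest on an unstated scoring of boxes that are neither exclusive nor exhaustive. At every month length from 28 to 31 days, five a month fits two boxes and six a week fits none. The weekly box spans about 4 to 22 a month and the top box is unbounded. The only assumption in these figures is the length of a month.

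The consequence is limited. The documents do not make follower outcomes depend on follower enrolment, which is optional; the study has no formal power; and neither primary endpoint is affected. It is worth correcting because it bears on a stated secondary objective and is cheap to put right.

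The Appendix F sign is best treated as a typographical error on a form in use, to be corrected in its own right.

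**What to change.** **Follower form and analysis: choose one.**
1. Replace the answers with exclusive, exhaustive bands on a single monthly scale, and state when not applicable should be ticked rather than never. In the Statistical Analysis Plan, replace the t-test with an ordinal comparison between arms.
2. Ask for the number of times this month and analyse it as a count. The downside is rounding and guessing at high frequencies.

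Under either option, because each follower answers monthly, state whether the analysis uses one summary per follower or models the repeated answers.

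**Forms already completed.** Flag the form version, analyse earlier answers as ordered categories, and write that rule down before the data are examined by arm.

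**Appendix F.** Change the parenthesis to >300 mg/dL so that it agrees with the item on values above 300, and flag the version.

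**Cost.** Two form edits on paper and in REDCap, a version flag, and a sentence or two in the Statistical Analysis Plan. Answers from before and after the change will not be fully comparable.

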Appendix F

BDC Pregnancy CGM Post-Partum Questionnaire

Subject ID: _____

Clinic Visit: (dd/mmm/yyyy) : _____ / _____ / _____

Post-Partum Week: ___4 to 6 weeks ___6 to 8 weeks ___8 to 10 weeks ___10 to 12 weeks

Pregnancy Outcome Date _____
(dd/mmm/yyyy)

Gestational Age _____ Birth Weight _____ Birth Length _____

Child is still living? Yes No Baby's Sex Male Female

Preterm labor during pregnancy? Yes No

If yes, please describe, including dates of hospital admissions: _____

Delivery type:

Vaginal If yes: Spontaneous Induced Breech Vacuum Forceps

VBAC If yes: Spontaneous Induced

Cesarean Section If yes: Low Transverse Low Vertical Classical Unspecified

Pregnancy complications? Yes No

If yes, check all that apply:

 Placenta previa	 Placenta accreta	 Incompetent cervix
 Hyperemesis gravidarum	 Proteinuria	 Hypoglycemic seizure
 Pregnancy-induced hypertension	 Oligohydramnios	 Polyhydramnios
 Pre-eclampsia	 Eclampsia	 Diabetic ketoacidosis
 HELLP syndrome	 Progression of diabetic complications	
 Small for gestational age baby	 Large for gestational age baby	
 Other _____		

Labor complications? Yes No

If yes, check all that apply:

 Fetal intolerance	 Anesthetic complications	 Pre-eclampsia
 Eclampsia	 Dysfunctional labor	 Seizures during labor
 Cephalopelvic disproportion	 Placental abruption	 Placenta previa
 Shoulder dystocia	 Breech delivery	 Nuchal cord
 Excessive bleeding	 Failure to progress in first stage	
 Failure to progress in second stage	 Other _____	

Neonatal complications? Yes No

If yes, check all that apply:

 Birth trauma/injury	 Hypoglycemia	 Asphyxia
 Jaundice	 Congenital anomalies _____	

Other _____

Was the baby admitted to the Neonatal Intensive Care Unit (NICU) for any length of time during your hospital stay? Yes No

If yes, please describe: _____

Are you or did you ever breastfeed after your baby was delivered? Yes No

If yes, check all that apply:

- Breastfed within the first week of baby's birth and not afterwards
- Breastfed within the first month of baby's birth and not afterwards
- Breastfed for the first 2 months after baby's birth and not afterwards
- Breastfed for the first 3 months after baby's birth and not afterwards
- Breastfed for the first 3 months after baby's birth and still breastfeeding
- Breastfed exclusively
- Breastfed and formula-fed the baby

Questions about glucose variability:

Have you had any glucose values below 50 within the last month? Yes No

If yes, how often on average?

- Every day
- A few times per week
- A few times per month
- Once

Over the last month did you have to do something to correct a low glucose (<50 mg/dL) or did someone else have to intervene for a low glucose on your behalf? Yes No

If yes, check all that apply:

- Consume glucose tablets or glucose gel
- Eat or drink something with carbohydrates
- Call health care provider for help
- Receive an injection of glucagon
- Receive an infusion of dextrose (glucose through a vein)
- Call to emergency services (like 911)
- Stay in the hospital for observation and/or treatment

If yes, when? _____ For how long? _____

Have you had any glucose values above 300 within the last month? Yes No

If yes, how often on average?

- Every day
- A few times per week
- A few times per month
- Once

Over the last month did you have to do something unusual (besides taking extra insulin) for a very high glucose (<300 mg/dL) or did someone else have to intervene for a very high glucose on your behalf?

Yes No

If yes, check all that apply:

- Take multiple insulin boluses within 6 hours to bring the glucose down
- Change an infusion set earlier than anticipated
- Drink extra amounts of fluids
- Call health care provider for help
- Call to emergency services (like 911)
- Receive insulin and/or fluids through a vein
- Stay in the hospital for observation and/or treatment

If yes, when? _____ For how long? _____

References:

